PT	Preferred Term
PUL	Performance Upper Limb
QTcF	QT corrected for HR using Fridericia's method
QTcB	QT corrected for HR using Bazett's method
SAE	Serious Adverse Event
SAP	Statistical Analysis Plan
SD	Standard Deviation
SOC	System Organ Class

SVC	Slow Vital Capacity
TEAE	Treatment Emergent Adverse Event

2 Introduction

This Statistical Analysis Plan (SAP) describes the statistical analyses to be conducted for study SNT-I-015, an exploratory phase I study of omigapil. The statistical methods were prospectively planned in the study protocol. This SAP was written during the study conduct and the authors and reviewers of the SAP had access to the study data. This SAP serves as documentation of statistical methods used to derive the endpoints and summarize the study data.

3 Study objectives

The study objectives were defined in the study protocol. The primary objective of the study is to establish the pharmacokinetic (PK) profile of omigapil in a range of doses in paediatric and adolescent patients with Congenital Muscular Dystrophy (CMD). The secondary objective is to evaluate the safety and tolerability of omigapil at a range of doses in paediatric and adolescent patients. The tertiary objective is to establish the feasibility of conducting disease-relevant clinical assessments in paediatric and adolescent patients with CMD to aid in the design of future studies.

4 Design and type of the study

Study SNT-I-015 is a phase I, open-label, sequential group, ascending oral dose, continual reassessment method (CRM) based model, PK, cohort study with patients randomly assigned to one of the three dose cohorts.

Dose levels were to be defined based on the following rules. Four subjects were to be treated at 0.02 mg/kg (level 1) daily for 12 weeks. In case of no toxicity, dose escalation would occur after every 4 subjects until one or more patients exceed the target AUC_{0-24h} range. When exceeding the target range, subsequent dose levels were to be determined from the observed PK. Subsequent patients were to be enrolled in groups of 4 using a CRM- type dose escalation/reduction design with the possibility to interpolate between pre-specified doses (Cheung, 2011). As a result, 4 dose levels of omigapil were used for the randomized groups in the following order, along the study, (0.02 mg/kg, 0.08 mg/kg, 0.04 mg/kg, 0.06 mg/kg).

Patients were stratified by disease type (Laminin Alpha 2-related dystrophy [LAMA2-RD] or Collagen 6-related dystrophies and myopathies [COL6-RD]) and weight and will be similarly represented. One patient was to be assigned from each stratum to each dose-escalating group (cohort), so that the cohorts will have similar representation of disease type and weight, to ensure comparable PK, safety, tolerability and efficacy feasibility assessment data.

5 Sample size considerations

A total of 16-20 evaluable patients were planned to be accrued using a CRM-type dose escalation/reduction design with the possibility to interpolate between pre-specified doses. The proposed dosing schedule adapts from a CRM-like algorithm called SAVOR (Cheung, Elkind, 2010) that aims to identify a dose exceeding AUC_{0-24h} of 33 ng h/ml with a probability of 10% or less. The upper end of the AUC_{0-24h} of 3-33 ng h/ml was targeted because animal modelling in

CMD-relevant models showed higher efficacy at 1 mg/kg compared to 0.1 mg/kg. By enrolling up to 20 patients, 8-12 subjects were to be assigned to the dose predicted to result in the target AUC_{0-24h} range (which may be less than the highest dose).

6 Analysis sets

6.1 Intention-to-treat (ITT) dataset

The ITT dataset will include all enrolled patients who received at least one dose of the study medication and completed at least one post-baseline assessment. The ITT dataset will be used for all analyses related to disease relevant clinical assessments.

6.2 Pharmacokinetic (PK) dataset

The PK dataset will include all enrolled patients who received at least one dose of the study medication and completed at least one PK assessment. However, a review of dosing information will be performed by the investigator to consider excluding data in any period or on any day where a subject was judged to have received <80 % or >120% of the scheduled dose of the investigational product. Plasma concentration data will be excluded if concentrations are extremely low relative to other subjects' data; in these cases plasma concentrations will be excluded from all or part of the profile, as appropriate. The PK dataset will be used for all PK analyses.

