- On daytime Non Invasive Ventilation (NIV)
- Intake of prohibited medication (as listed in Appendix I)
- Anticipated need for anesthesia during the course of this study
- Patients with renal impairment defined as urinary protein concentration ≥ 0.2 g/L
- Patients with moderate to severe hepatic impairment.
 - ALT $\geq 8x$ upper limit of normal (ULN) and total bilirubin $2x$ ULN (plus $>35\%$ 'direct' bilirubin), or
 - ALT $\geq 8x$ ULN and INR >1.5 or ALT $>2x$ baseline levels, and total bilirubin $> 2x$ ULN (plus $>35\%$ 'direct' bilirubin),
 - or
 - ALT $>2x$ baseline levels, and INR greater than 1.5,

	
• or• ALT ≥ 8 x ULN and associated with symptoms of hepatitis (e.g. onset or worsening of nausea, anorexia, jaundice or abdominal pain) or hypersensitivity (e.g. fever, rash, eosinophilia),• or• GGT > 2-3x ULN and bilirubin 2x ULN (plus >35% 'direct' bilirubin) or• GGT >2-3x ULN and INR >1.5
Participation Period	28 weeks per patient – up to 4 weeks screening, 4 weeks vehicle (Humco® Cherry Syrup) run-in phase followed by 12 weeks on omigapil and a follow-up visit 8 weeks after last dose.
Study Design	
This study will be an open-label, sequential group, ascending oral dose, continual reassessment method (CRM) based model, pharmacokinetic, cohort study.
 
A Data and Safety Monitoring Board (DSMB) will be established to monitor patient safety throughout the study.

Pharmacokinetics	
Pharmacokinetic (PK) parameters of omigapil and metabolites, such as C_{max}, C_{min}, t_{max}, $t_{1/2}$, AUC_{0-t}, AUC_{0-8h}, AUC_{0-24h}^*, λ_z and R_o (*if sufficient data are available) will be calculated.
 
• During the first 8 hours following initial intake of the study medication (Visit 2) 
and
 
• After 4 weeks of daily dosing, during 8 hours following study medication intake (Visit 3) 
and
 
• After 12 weeks of daily dosing, during 8 hours following study medication intake (Visit 5)• On each occasion, 7 blood samples (1 pre-dose and 6 post-dose time points at 0.5, 1, 1.5, 2, 4, and 8 hours) will be collected; (3 ml per sample; 21 ml per visit).

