Patients will have the possibility to perform the screening and baseline visits combined or within a period of less than 6 days in order to allow for the laboratory results to be available to confirm patient eligibility. Up to 7 study visits will be required: Screening; Visit 1 - Baseline/initiation of run-in phase; Visit 2 - Week 4/ initiation of omigapil dosing; Visit 3 - Week 8 after 4 weeks of omigapil dosing; Visit 4 – Week 12 after 8 weeks of active treatment; Visit 5 – Week 16 after 12 weeks of omigapil dosing; Visit 6 – Week 24, Follow-Up visit, 8 weeks after stopping the drug.

Patient management will be the same for all three Cohorts.

- At Screening, which should take place no more than 4 weeks prior to Baseline/Visit 1, written informed consent/assent will be obtained and the eligibility of the patient will be assessed. For further details on procedures that will be done at this visit, see Section 4.3.3.
- At Visit 1/ Baseline (or Screening/Baseline if the visits are combined or within 6 days of each other to allow for all information to confirm eligibility to be available such as laboratory results) patients will undergo the safety evaluations and efficacy feasibility assessment tests if the patient is capable of performing them. Patients will be dispensed a 4-weeks supply of vehicle (Humco® Cherry Syrup) and given an appointment for Visit 2 (Day 1 of omigapil dosing). AEs will be collected during this run-in period for comparative purposes. To assist with AE capture and dosing compliance, patients and/or their caregivers will be asked to maintain a diary card (See Appendix H) throughout the study period. This will be reviewed at each visit. For further details on procedures that will be done at this visit, see Section 4.3.4.
- At Visit 2/ Week 4, patients will repeat the safety evaluations. The first dose of omigapil will be given during this visit and PK sampling will also be initiated.
 - Blood samples for PK will be taken pre-dose and at 0.5, 1, 1.5, 2, 4, and 8 hours post-dose.
 - Vital signs and oxygen saturation using a pulse oximeter will be monitored throughout the day and patients monitored for treatment emergent adverse events.
 - Patients will be dispensed sufficient omigapil for 4 weeks of omigapil dosing.
- Interim Calls: A safety follow-up call will be made in weeks 5, 6 and 7 (after approximately 1, 2 and 3 weeks of starting omigapil dosing) to elicit reporting of any treatment emergent adverse events.

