There will be no placebo group and assessment of safety and tolerability will include analysis of relevant data from the run-in periods for all cohorts.

Incidences of AEs/SAEs, severity and relationship of AEs/SAEs to study medication, and early withdrawal due to AEs/SAEs will be summarized using frequencies and percentages for each dose level of study medication and for the run-in periods. Incidences, laboratory abnormalities and physical examination results will be presented by visit for each dose level of study medication. ECG parameters will be summarized for each dose level using descriptive statistics.

- Pharmacokinetic parameters C_{max}, C_{min}, t_{max}, t_{1/2}, AUC_{0-t}, AUC_{0-8h}, AUC_{0-24h}*, λ_z, and R_o (*if sufficient data are available) will be

calculated and summarized by dose level of study medication using descriptive statistics.

Details of the planned analyses of the PK samples will be included in a separate Pharmacokinetic Analysis Plan.

Details of the planned analyses of the safety and efficacy data from the efficacy feasibility assessments will be outlined in a separate Statistical Analysis Plan.

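### SAP 6.2 excludes extremely low concentrations by their value alone, with no cut-off, cause or defined comparison group; where a whole low profile is genuine, this biases dose-level mean AUC and Cmax upward

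*SAP*

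**What the plan says.** SAP 6.2 builds the PK dataset from enrolled patients with at least one dose and one PK assessment, and then sets two exclusions.

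- **Dosing.** "a review of dosing information will be performed by the investigator to consider excluding data" where a subject is judged to have had under 80% or over 120% of the scheduled dose. This rule is two-sided, has limits, names who decides and is discretionary.
- **Low concentrations.** "Plasma concentration data will be excluded if concentrations are extremely low relative to other subjects" (their data being the comparator); "in these cases plasma concentrations will be excluded from all or part of the profile, as appropriate". This rule is mandatory and one-sided, and 6.2 does not tie it to the dosing review.

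The section ends: "The PK dataset will be used for all PK analyses". The protocol synopsis makes the PK profile the primary endpoint. Its Statistical Methods say that the parameters will be "calculated and summarized by dose level of study medication using descriptive statistics". Planned group sizes are 4, 4 and 8–12. SAP 4 reports that "4 dose levels of omigapil were used for the randomized groups in the following order": 0.02, 0.08, 0.04 and 0.06 mg/kg. SAP 11 refers PK parameter analysis to a PK Analysis Plan (Appendix 18.3), which is not in the text available for this review. SAP 18.2 plans a PK data listing (16.2.5.1).

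**The concern.** The low-concentration rule selects on the outcome being described. Patients who absorb little are part of the PK profile that the study sets out to establish, and as worded the rule can remove a profile from a patient who was dosed correctly. At Visit 2 a missed dose is an unlikely explanation, because "The first dose of omigapil will be given during this visit and PK sampling will also be initiated". Vomiting or a sample or assay failure remains possible, but 6.2 does not ask for evidence of either.

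Three things are left open: how low is extremely low, who the comparators are, and when the whole profile goes rather than part of it. SAP 2 records that its authors and reviewers had access to the study data, so an objective criterion matters more than usual. At stake are the dose-level means of AUC and Cmax in small groups.

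**Working it through.** The documents state no bias, variability or cut-off for this rule, so there is no figure to reproduce. The check covers direction, then size.

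**Inputs from the documents.** Group sizes n = 4, 8, 12 (protocol synopsis, 4, 4 and 8–12 patients). Sampling: "7 blood samples (1 pre-dose and 6 post-dose time points at 0.5, 1, 1.5, 2, 4, and 8 hours) will be collected" at each of Visits 2, 3 and 5.

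**Assumed inputs.** Lognormal exposure with between-patient log-SD 0.4 to 0.8, i.e. CV = √(exp(SD²) − 1) = 42% to 95%. Cut-offs of one-tenth, one-fifth and one-third of the group median at one visit.

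**1. Direction, whole profile, within one dose level.** Dropping a value x below the group mean m gives

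new mean = m + (m − x)/(n − 1), which exceeds m.

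The shift is certain. It is a bias only if x is a genuine exposure.

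**2. Size when one profile is lost.** Let n − 1 patients share a value of 1 and one patient have 0.2.

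- Arithmetic mean before: (n − 0.8)/n; after: 1. Ratio n/(n − 0.8): 4/3.2 = 1.25; 8/7.2 = 1.11; 12/11.2 = 1.07. Rises of 25%, 11% and 7%.
- Geometric mean ratio 5^(1/n): 1.50, 1.22, 1.14. Rises of 50%, 22% and 14%.

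**3. Expected size when all values are genuine.** Simulation of 200,000 groups per setting, dropping values below the cut times the group's own median. The table gives the average rise of the arithmetic mean, with the share of groups that lose anyone in brackets.

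| Cut | log-SD | n = 4 | n = 8 | n = 12 |
|---|---|---|---|---|
| 1/5 | 0.4 | 0.01% (0.04%) | 0.01% (0.05%) | 0.01% (0.07%) |
| 1/5 | 0.6 | 0.6% (2%) | 0.5% (4%) | 0.4% (5%) |
| 1/5 | 0.8 | 2.8% (9%) | 2.4% (17%) | 2.3% (24%) |
| 1/10 | 0.8 | 0.4% (1.3%) | 0.3% (2.2%) | 0.3% (2.9%) |

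At a one-fifth cut the geometric mean rises by 0–7% on average. At log-SD 0.8 and the same cut, groups that do lose someone see the arithmetic mean rise by about 30%, 14% and 9% for n = 4, 8 and 12. A cut of one-third would give about 8% on average at log-SD 0.8 and n = 8, but that is a loose reading of extremely low. The undefined cut-off therefore drives the answer.

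**4. Part of a profile.** Take a one-compartment curve (assumed ka 1.5/h, ke 0.25/h), the protocol's sampling times and the linear trapezoid, with one sample at a tenth of its proper value.

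- Low 2 h sample: AUC(0–t) is 22% below the undisturbed value if kept and 1% below if deleted. Deletion moves it up.
- Low 8 h sample: 9% below if kept and 35% below if deleted, because the curve then ends at 4 h. Deletion moves it down.

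Partial exclusion therefore has no fixed direction.

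**The case against.** **Section 6.2 only defines a dataset.** A cut-off and a cause could sit in the PK Analysis Plan. This is fair, and it limits the point to 6.2. But 6.2 does not refer to that plan for the criterion, and its own sentence is an instruction.

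**Excluding a failed dose or sample is good practice.** This stands. Dropping such a profile removes an error, so a reader who infers that every use of the rule biases the mean goes too far. The fault is that 6.2 does not separate the two cases. The compliance check in SAP 10 cannot do so either: it rests on bottle volume since the previous visit and would not show a failed dose on the sampling day.

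**The effect is small and rests on assumptions.** This also stands. The 25% figure supposes that the event has happened. It also concerns one visit's summary, since each patient has three PK occasions and may keep the other two.

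A reader might infer stronger things that the documents do not support:

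- *Dose assignment was affected.* Nothing says that the 6.2 dataset was the one used for dosing decisions, and removing low values does not change how many patients exceed 33 ng.h/mL.
- *Between-patient spread is understated.* In affected groups at log-SD 0.8 and a one-fifth cut, the log-SD falls from 1.22, 0.99 and 0.92 to 0.61, 0.70 and 0.72. Each of these is nearer the true 0.80 than before, so this does not show harm.
- *Low-dose patients would be dropped by comparison with higher doses.* The wording permits it, but PK is summarised by dose level and this is a strained reading. It is a reason to define the comparators and no more.
- *Patients below 3 ng.h/mL would be hidden.* The available text plans no table of attainment of the 3–33 range.
- *The rule was written to remove known results.* Access to the data is stated. No such exclusion is.

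**Conclusion.** Wrong as written, minor severity. The rule is mandatory, low-side and triggered by value. Its cut-off, cause and comparison group are not stated in 6.2, and it governs the dataset for the primary endpoint.

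The upward bias in mean AUC and Cmax is conditional on the low profile being genuine, dropped whole, and compared within its dose level. Under those conditions the loss of one profile can matter in groups of four, while the expected effect is at most about 3% at a one-fifth cut. These sizes rest on the assumed cut-offs and variability above. The conclusion would change if the PK Analysis Plan already restricts the rule.

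**What to change.** In SAP 6.2, replace the low-concentration sentence with wording to this effect:

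- Primary PK summaries use all concentrations except those with a documented cause independent of the value: recorded dosing error, vomiting, or sample or assay failure.
- A sensitivity summary also excludes extremely low profiles, using a stated cut-off applied within dose level and visit (for example, below one-fifth of the median there).
- Each exclusion is listed with patient number, visit, samples and reason.

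If Appendix 18.3 already limits the rule in this way, cite it in 6.2 and delete the conflicting sentence.

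The cost is one paragraph, one listing and one extra table. The real downside is that unrecorded dosing failures stay in the primary summary, giving somewhat lower means and higher variability. The sensitivity summary shows how much they matter.

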6.3 Safety dataset

The Safety dataset will include all enrolled patients who received at least one dose of study medication. Safety dataset will be used for all the safety analyses.

7 Disposition of patients

The number of patients enrolled into the study at screening, the number of patients who failed the screening and the reasons for screening failures will be summarized. The number of patients entering and completing the study will be summarized by dose level and overall. Also, the number of patients who discontinued prematurely, the reasons for premature discontinuations and replacement information will be summarized by dose level and overall. The disposition data will also be presented in a listing format.

8 Demographic and other baseline characteristics

All demographic and other baseline characteristics (age, height, weight, body mass index [BMI], gender, ethnicity, race, child-bearing potential, ambulatory status, disease type (LAMA2-RD or COL6-RD), time since CMD diagnosis and use of respiratory aid [Bi-Pap]) will be listed by dose level and summarized with descriptive statistics by dose level. The physical examination findings, medical history and pregnancy test results will be listed by dose level.

Age will be calculated using month of birth and month of baseline (screening) visit as difference in months between baseline and time of birth divided by 12. Height will be estimated from ulna length by using the following formulas (Gauld, 2003, 2004):

$$\text{Height (male, age <20)} = ((4.605 * \text{ulna length [cm]}) + (1.308 * \text{age [years]}) + 28.003$$

Height (female, age < 20) = ((4.459* ulna length [cm]) + (1.315 * age [years])) + 31.485.

Height and weight will also be presented as percentages of normal growth at the age of the patient (Clinical Growth Charts, U.S. National Center for Health Statistics).

9 Concomitant medication/treatment

Concomitant medication and treatments are coded to WHO drug dictionary version September 2017, and will be listed by dose level, including the Preferred term and ATC classification levels 1 and 4.

10 Extent of exposure and compliance

The extent of exposure will be summarized based on the duration of study treatment (days). The duration of study treatment will be listed and summarized with descriptive statistics by dose level.

Compliance will be evaluated as percentage of the daily doses taken (calculated from the estimated volume withdrawn from the bottle and daily dosing volumes) since previous visit. Patients with compliance of 80-120% are considered as compliant. The compliance (as %) will be listed by dose level. In addition, the proportion of compliant patients will be tabulated by dose level.

11 Pharmacokinetics

The analysis of the PK parameters is described in a separate PK Analysis Plan (Appendix 18.3).

12 Analysis of safety and tolerability

12.1 Adverse events

All recorded adverse events (AEs) will be coded according to the Medical Dictionary for Regulatory Activities (MedDRA version 20.1). All treatment emergent AEs (TEAEs), i.e. events starting or worsening during study treatment or follow-up will be listed by dose level and tabulated by dose level, system organ class (SOC) and preferred term (PT). Both patient and event counts will be included in the tabulations. In addition, tabulations by severity and causality will be provided. Serious TEAEs (SAEs) and TEAEs leading to discontinuation of study treatment will be summarized as data listings. The AEs occurring during the run-in period will be listed separately.

Adverse events of special interest (AESI) will be summarized by dose level, SOC and PT. Also a listing with PFT information from all visits during the study will be presented together with the AE information for subjects experiencing AESI. The following preferred term will be considered as AESI: Pulmonary function test decreased.

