14.2.2 Adverse events

Table 14.2.2.1 Summary of all adverse events

Table 14.2.2.2 Treatment emergent adverse events by SOC and PT

Table 14.2.2.3 Treatment emergent adverse events by PT

Table 14.2.2.4 Treatment emergent adverse events by PT and severity

Table 14.2.2.5 Treatment emergent adverse events by PT and causality

Listing 14.2.2.6 Serious treatment emergent adverse events

Listing 14.2.2.7 Treatment emergent adverse events leading to discontinuation of study treatment

Table 14.2.2.8 Treatment emergent adverse events of special interest

Listing 14.2.2.9 Run-in emergent adverse events

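### SAP 12.1 replaces the protocol's promised summary of run-in adverse events with a listing, and section 14 does not declare the change

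*SAP*

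**What the plan says.** The protocol synopsis sets out the role of the run-in under Statistical Methods: "There will be no placebo group and assessment of safety and tolerability will include analysis of relevant data from the run-in periods". It then says that the incidence of AEs and SAEs, their severity and relationship, and early withdrawal because of them "will be summarized using frequencies and percentages for each dose level of study medication and for the run-in periods". Study Procedures, at Visit 1, give the purpose of recording these events: "AEs will be collected during this run-in period for comparative purposes".

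SAP 12.1 tabulates treatment-emergent events (TEAEs), meaning those that begin or worsen on treatment or in follow-up. For the run-in it says: "The AEs occurring during the run-in period will be listed separately". For the serious and discontinuation categories it says: "Serious TEAEs (SAEs) and TEAEs leading to discontinuation of study treatment will be summarized as data listings". The output plan in SAP 18.1 carries "Listing 14.2.2.9 Run-in emergent adverse events" and no table named for the run-in. It also carries "Table 14.2.2.1 Summary of all adverse events", of which only the title is given. SAP section 7 adds that "the reasons for premature discontinuations and replacement information will be summarized by dose level and overall".

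SAP section 14, which records departures from the protocol, names one: the per-protocol analysis is dropped. SAP section 2 says that the methods were planned in the protocol and that the SAP's authors and reviewers could see the study data.

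**The concern.** Safety and tolerability is the secondary objective. Some AEs will occur in these patients without omigapil, and with no placebo arm the run-in is the pre-omigapil period against which the TEAE tables can be read. A listing shows each event but gives no percentage, no denominator and no overall figure to set beside those tables. Followed as written, SAP 12.1 leaves out a summary that the protocol committed to.

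The missing declaration matters separately. Section 14 exists to record such changes and section 2 ties the methods to the protocol, so a reader will assume that nothing else was altered.

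**Working it through.** There is no published figure to reproduce. The check is a comparison of texts, followed by arithmetic on what a restored summary would need.

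**1. Promise against delivery.**

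| Item | Protocol synopsis | SAP |
|---|---|---|
| Run-in AEs | Frequencies and percentages | Listing 14.2.2.9 |
| SAEs, by dose level | Frequencies and percentages | Listing 14.2.2.6 |
| Withdrawal due to AE, by dose level | Frequencies and percentages | Listing 14.2.2.7; section 7 tabulates reasons for discontinuation, categories not named |
| Declared in section 14 | – | No |

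**2. Denominator.** SAP 6.3 puts in the Safety dataset only patients with at least one dose of study medication. The Pharmacokinetics part of the synopsis places the first intake of study medication at Visit 2, after the run-in. The SAP does not say whether vehicle counts. If it does not, a patient who leaves during the run-in is in no analysis set. Hypothetically, 4/20 = 20% with a run-in AE becomes 5/21 = 24% if one such patient had an AE and is counted, and 7/23 = 30% if three did.

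**3. Unequal windows.** The synopsis gives 4 weeks of run-in, 12 of treatment and 8 of follow-up, so the TEAE window is 12 + 8 = 20 weeks. The documents give no AE rates, so the rates below are assumptions: constant over time, with no drug effect. P(at least one AE) = 1 − exp(−rate × weeks).

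| AEs per patient-week | 4 weeks | 12 weeks | 20 weeks | Ratio 12:4 |
|---|---|---|---|---|
| 0.02 | 7.7% | 21.3% | 33.0% | 2.8 |
| 0.05 | 18.1% | 45.1% | 63.2% | 2.5 |
| 0.10 | 33.0% | 69.9% | 86.5% | 2.1 |

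Raw percentages would suggest a two- to three-fold excess on omigapil where none exists.

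**4. Small counts.** Expected run-in events = rate × 4 weeks × n. For a dose group of 4 this is 0.32, 0.8 or 1.6. For 20 patients it is 1.6, 4 or 8. At 0.05 per patient-week, 20 patients give 0.05 × 80 = 4 run-in events and 0.05 × 240 = 12 on treatment. The rate ratio is 1.0, with exact conditional 95% CI 0.30 to 4.25. With 24 events on treatment it is 2.0 (0.69 to 7.93).

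**5. Unequal questioning.** The synopsis schedules one contact in the 4 run-in weeks (Visit 2), or 1/4 = 0.25 per week. On omigapil there are nine calls plus Visits 3, 4 and 5, or 12/12 = 1.0 per week. If the run-in captured 75% or 50% of what is captured on omigapil (assumed), no drug effect would appear as a rate ratio of 1/0.75 = 1.3 or 1/0.50 = 2.0. The diary card, kept throughout, limits this.

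**The case against.** The strongest reply is that nothing is lost. The run-in events are listed, visit dates and first-dose dates are in Listings 16.2.1.7 and 16.2.2.2, and disposition is tabulated, so a reader could rebuild counts and time at risk. Table 14.2.2.1 refers to all adverse events, while the titles next to it say treatment emergent, so it may include the run-in. The synopsis leaves the detail of the safety analysis to the SAP. The counts are also too small to settle anything, and relationship to omigapil means little before the first dose.

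Much of this stands. The data survive, the comparison would be imprecise, and a run-in breakdown by preferred term, severity and causality within each dose level would be almost empty. It does not remove the mismatch. A table title is not a commitment to a run-in column, and leaving detail to the SAP does not cover dropping a promised summary without a declaration.

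Three stronger readings should be resisted.
- A reader might infer that the run-in safety data will be missing from the report. The listings show otherwise.
- A reader might infer that the summary was dropped because the authors had seen the data. The SAP discloses that access, but nothing in the documents links it to this choice.
- A reader might infer that SAP 12.3 offers no ECG comparison between an omigapil-free value and a post-dose value. At Visit 2 the within-visit change starts from an omigapil-free reading. Abnormal QTc results also go into shift tables by visit and time point, which may well compare post-dose readings with baseline. Only the reference for the >30 and >60 ms changes is unstated, which is an ambiguity and not a shown error.

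**Conclusion.** The point holds and should be corrected, although it does not threaten the trial's conclusions. SAP 12.1 gives a listing where the protocol synopsis promises run-in frequencies and percentages. It does the same for serious TEAEs and for TEAEs leading to discontinuation. Section 14 declares neither. The loss is a planned descriptive summary for the secondary objective.

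Restoring percentages alone would mislead, because the windows differ in length and in how often patients are asked about events. The 2.1- to 2.8-fold figure depends on the assumed rates of 0.02 to 0.10 per patient-week, held constant.

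Two limits apply. Only the protocol synopsis was available, so the full statistical section could not be checked. The synopsis refers to its header for the version date, so it could not be matched to the protocol of 01-Dec-2017 in the SAP's reference list.

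**What to change.** 1. In SAP 12.1 and Table 14.2.2.1, add a run-in column, overall and by dose level, with patients n (%) and events for any AE, SAE, severity and AE leading to withdrawal. Give SOC and preferred term for the run-in overall only. Add count rows for serious TEAEs and TEAEs leading to discontinuation. If run-in causality is left out as uninformative, say so in section 14.
2. Use all patients who started the vehicle run-in as the run-in denominator, and state whether vehicle counts as study medication.
3. Show events per patient-week, or compare matched 4-week windows.
4. Label the comparison descriptive, and footnote that scheduled weekly calls apply on omigapil only.
5. If Table 14.2.2.1 is already meant to do this, describe its content. If only the listings are kept, declare that in section 14.

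A minor addition: in 12.3, state the reference value for the QTc >30 and >60 ms changes, preferably one omigapil-free baseline.

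The cost is SAP wording and one extended descriptive table from data already collected. The drawback is sparse run-in cells and an imprecise comparison, which the descriptive label makes plain.
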